4.0 TREATMENT PLAN

This is a single arm phase Ib/II study in which patients will be treated with uproleselan given intravenously, combined with cladribine, (2-CDA, given intravenously [IV]) in combination low dose cytarabine (LDAC, given subcutaneously [SQ]) as induction therapy, followed by up to 6 cycles of consolidation/maintenance therapy composed of 2-CDA + LDAC (according to schema below) also in combination with uproleselan. In patients who do not achieve CR/CRi/MLFS after cycle 1, an additional course of re-induction with 2-CDA+LDAC+uproleselan may be given.

Treatment will be continued during the duration of the study unless patient exhibits evidence of clinically significant treatment failure, clinically significant disease progression, unacceptable toxicity, or if the investigator determines that discontinuation is in the best interest of the patient. Patients who do not achieve at least MLFS after two cycles of therapy will be taken off study. Relapsing patients may remain on the study if participation in the study is still providing disease control or clinical benefit and is considered in the best interest of the patient after discussion with the principal investigator.

Patients will be treated with the study drugs per protocol, based on the calculation of the patient's body surface area (BSA). The BSA will be calculated before each cycle and will be based on the patient's height and weight.

Patients will be instructed to self-administer cytarabine at home unless hospitalized and return unused drug in accordance with institutional guidelines. All induction and consolidation intravenous infusions will be administered at MD Anderson Cancer Center (MDACC) or at the MDACC Houston Area Locations (HALs).

The primary objective is to determine the safety of this combination and also to determine efficacy in achieving CR, CRi; and prolonging RFS and OS. All patients will be registered for the protocol via the Clinical Oncology Research (CORE) system at MDACC (single institution study).

The study will have 2 dose levels during lead-in, followed by an expansion cohort of 25 patients at the safe and tolerable dose level. All patients will be treated with the RP2D of uproleselan of 800 mg IV on D1 and then IV q12 hours on D2-12.

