4.3 Duration of Therapy

In the absence of treatment delays due to adverse events, the treatment will be administered approximately once every 4 weeks for up to 6 cycles. The patient will continue on the study unless one of the following criteria applies:

- Clinically significant progressive disease as defined by Modified International Working Group Criteria (see section 9) without evidence of clinical benefit. (Patients who have not had at least 50% reduction in bone marrow blasts by 4-6 cycles would be considered not to have clinical benefit and will come off study).
- Possibility of undergoing allogeneic bone marrow transplant.
- Intercurrent illness that prevents further administration of treatment.
- Patient request.
- Unacceptable toxicity.
- Need for further, alternative treatment.
- General or specific changes in the patient's condition that render the patient unacceptable for further treatment in the judgment of the investigator or treating physician.

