5.3 Outcome assessments

- a. Bone marrow aspiration and/or biopsy starting on day 21 (+/- 7 days) of therapy and then every 2 weeks (+/- 7 days) as required by leukemia evolution until remission or non-response. Bone marrow tests may be ordered more frequently as indicated by changes in peripheral blood counts. No repeat bone marrow is necessary if non-response or progressive disease can be unequivocally diagnosed from peripheral blood tests or, in patients with a

WBC <0.4 x10⁹/L, if the bone marrow is considered non-contributory by the investigator at any point.

b. Patients will be followed for relapse and survival every 6 to 12 months after completion of active treatment and while still on study or be enrolled on the leukemia department long-term follow-up umbrella protocol. This may be completed by phone call if the patient is not coming for routine visits.

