Multi Lean Desktop (version 2.1.0) was used to generate the toxicity and futility stopping boundaries and the operating characteristics table.

ANALYSIS PLAN

Summary statistics will be provided for continuous variables. Frequency tables will be used to summarize categorical variables. The overall response rate will be estimated along with the 95% credible interval. Similar analyses will be performed for other binary outcomes such as CR, CRi, etc. Overall survival (OS) is defined as the time interval between treatment start and the date of death or last follow-up, whichever occurred first. Remission duration (CRd) is defined, within patients who achieve CR/CRi, the time interval between the date of CR/CRi and the date of disease relapse, death or last follow-up, whichever occurred first.

Progression-free survival (PFS) is defined as the time interval between treatment start and the date of death, relapse or last follow-up, whichever occurred first. Kaplan-Meier method will be used to assess OS, CRd and PFS probabilities. Data from all subjects who receive any study drug will be included in the safety analyses. Subjects who entered the study and did not take any of the study drugs and had this confirmed will not be evaluated for safety. The severity of the toxicities will be graded according to the NCI CTCAE v5.0 whenever possible. We will follow standard reporting guidelines for adverse events. Safety data will be summarized by category, severity and frequency.

Cohort Summaries

The Investigator is responsible for completing toxicity summary reports and submitting them to the IND office Medical Affairs and Safety Group, for review and approval. These should be submitted as follows:

Phase 1B:

After the first 3 evaluable patients, complete cycle 1 of study treatment, and every 3 evaluable patients thereafter, prior to expanding/changing dose levels, or opening Phase II.

Phase II:

After the first 5 evaluable patients per cohort, complete cycle 2 of study treatment, and every 5 patients thereafter, until enrollment is complete.

A copy of the summary report should be placed in the Investigator's Regulatory Binder under "sponsor correspondence".

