9.0 MEASUREMENT OF EFFECT

9.1 Criteria for Response

9.1.1 Definitions

Evaluable for toxicity. All patients will be evaluable for toxicity from the time of their first treatment on study.

Evaluable for response. Patients who have received at least one cycle of therapy, and have had their disease re-evaluated will be considered evaluable for response. These patients will have their response classified according to the definitions stated below. (Note: Patients who exhibit objective disease progression prior to the end of cycle 1 will also be considered evaluable.)

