9.1.8 Relapse-free survival (RFS)

Time from CR or CRi until the date of first objective documentation of disease-relapse or death.

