9.1.10 Disease progression

Progression will be defined as recurrence of the disease necessitating change in therapy, or failure to respond to therapy requiring change in treatment.

10. REGULATORY AND REPORTING REQUIREMENTS**10.1 Regulatory and Reporting Requirements**

CTCAE term (AE description) and grade: The descriptions and grading scales found in the CTEP Version 5 of the NCI Common Terminology Criteria for Adverse Events (CTCAE) will be utilized for AE reporting. The CTEP Version 5 of the CTCAE is identified and located on the CTEP website at: http://ctep.cancer.gov/protocolDevelopment/electronic_applications/ctc.htm. All appropriate treatment areas should have access to a copy of the CTEP Version 5 of CTCAE.

Refer to Section 10.2 for Leukemia-Specific Adverse Event Recording Guidelines. AE data will be collected in Prometheus

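### PFS in section 8.0 leaves out failure to respond, so a patient who never responds has PFS equal to OS

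*Combined protocol and SAP*

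**What the plan says.** All references are to the combined protocol and SAP.

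- **Section 8.0, Analysis Plan.** "Progression-free survival (PFS) is defined as the time interval between treatment start and the date of death, relapse or last follow-up", whichever is first. OS starts at the same point and is censored at the same point, with death as its only event. Remission duration (CRd) is confined to patients in CR/CRi and counts relapse or death. All three are summarised by Kaplan-Meier.
- **Section 1.0.** PFS is a named secondary objective.
- **Section 9.1.10.** Progression has two limbs: recurrence that forces a change of therapy, and "failure to respond to therapy requiring change in treatment".
- **Section 9.1.8.** RFS runs as follows: "Time from CR or CRi until the date of first objective documentation of disease-relapse or death".
- **Patients who fail treatment are foreseen.** Section 4.0: "Patients who do not achieve at least MLFS after two cycles of therapy will be taken off study". Section 4.3 ends participation for clinically significant progressive disease and points to section 9 for its definition. Section 9.1.1: "Patients who exhibit objective disease progression prior to the end of cycle 1 will also be considered evaluable".
- **Relapsing patients, section 4.0.** "Relapsing patients may remain on the study if participation in the study is still providing disease control or clinical benefit".
- **Assessments, section 5.3.** Item a repeats the marrow "as required by leukemia evolution until remission or non-response" and accepts peripheral blood where that settles the matter. Item b follows patients after active treatment for relapse and survival only.

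**The concern.** The endpoint is called progression-free survival, the protocol defines progression, and the endpoint does not use that definition. The recurrence limb of 9.1.10 overlaps with relapse. The failure-to-respond limb has no counterpart in section 8.0.

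A patient with refractory disease who is taken off study and moved to another therapy would therefore be counted as progression-free until death or last contact. For such patients PFS adds nothing to OS, and it is as long as or longer than a PFS that counts failure to respond. In a single-arm trial in a population with low expected response, readers will take the Kaplan-Meier PFS curve at face value. They may also set it beside PFS from studies that do count refractory disease.

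A smaller gap is that the plan does not say whether recurrence after PR or MLFS, without CR/CRi, is a PFS event.

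**Working it through.** **1. The definitions side by side.** Measure all times from treatment start: D = death, R = relapse, C = last follow-up, F = failure to respond requiring a change in treatment.

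- OS as written = min(D, C)
- PFS as written = min(D, R, C)
- PFS with the missing limb = min(D, R, F, C)

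The first two differ only through R. Where the plan uses relapse as an endpoint event (CRd in 8.0, RFS in 9.1.8), it follows CR or CRi. A patient who never responds has no R, so PFS = min(D, C) = OS. Adding F can only leave PFS unchanged or shorten it.

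The direction is claimed for never-responders only. Section 8.0 counts any relapse, 9.1.10 counts only recurrence that forces a change of therapy, and section 4.0 lets some relapsing patients stay on study. Replacing relapse by 9.1.10 could therefore delay events in that group, so the limb should be added to relapse, not put in its place.

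**2. How many patients could be affected.** Inputs from section 8.0: 25 phase II patients, CR/CRi 35% expected and about 45% targeted, with 11 of 25 as the worked case. Check on that case: a Beta(1,1) prior with 11 of 25 gives a Beta(12, 15) posterior with 95% interval 0.266 to 0.631, which reproduces the stated 0.27 to 0.63.

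- Target: 25 − 11 = 14 without CR/CRi (1 − 0.45 = 55%)
- Expected: 25 × (1 − 0.35) = 16.25, about 16 (65%)

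These are ceilings. Some of these patients reach PR or MLFS and might be recorded as relapsing, and some die before failure is declared.

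**3. Allowing for early death.** Section 2.12 gives 8-week mortality of 19% and 22% on lower-intensity therapy in ts-AML. Assume this applies here and that every such death is in a non-responder. Deaths are then 25 × 0.19 = 4.75 to 25 × 0.22 = 5.5.

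| Without CR/CRi | Less 5.5 deaths | Less 4.75 deaths |
|---|---|---|
| 14 | 8.5 | 9.25 |
| 16.25 | 10.75 | 11.5 |

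So about 8.5 to 11.5 of 25 would be alive without CR/CRi at 8 weeks, the nominal length of the two-cycle response window. The number is higher if some early deaths are in responders.

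**4. How far the curve could move.** The documents do not give this. For never-responders, the gap between the two PFS curves at time t is the proportion who have failed by t and are still alive. Its ceiling is (1 − ORR) × S(t), where S is survival in non-responders.

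As an illustration only, assume exponential survival with a median of 3, 4.2 or 6 months. The 4.2 is the overall ts-AML median in section 2.12; the 3 and 6 are assumed values on either side. Assume also that every surviving non-responder has changed treatment by 6 months. Then S(6) = 0.5^(6/median) = 0.25, 0.37 or 0.50.

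- At ORR 45%: 0.55 × S(6) = 0.14, 0.20 or 0.28
- At ORR 35%: 0.65 × S(6) = 0.16, 0.24 or 0.33

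Under these assumptions, 6-month PFS as written could exceed the corrected figure by up to 14 to 33 percentage points.

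**The case against.** **Relapse may have been meant loosely.** The word has no definition of its own, the CR/CRi anchor comes from other endpoints, and a reader might let 9.1.10 explain what progression-free means. But nothing in section 8.0 points to 9.1.10, and 9.1.10 itself separates recurrence from failure to respond. What stands is that the equality of PFS and OS is the literal reading. If the wider meaning was intended, the plan still has to say so, or two analysts could draw different curves from the same data.

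**The counts are soft.** Not reaching CR/CRi is not the same as never responding, and the limb also requires a change of treatment. The 8-week mortality comes from a lower-intensity group whose CR/CRp rates were 11% and 22%. Section 2.3 reports CR/CRp of 47% and 4-week mortality of 3% for cladribine/LDAC-based therapy in ts-AML. Those figures give 25 × 0.53 = 13.25 without CR/CRp, less 25 × 0.03 = 0.75 deaths, so 12.5 alive at 4 weeks if all deaths are in non-responders. Cycles may also start 4 to 7 weeks apart, so the real window can exceed 8 weeks. All of this stands: 8.5 to 11.5 is a conditional estimate, not a bound. It does not make the affected group small.

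**The endpoint could be renamed instead.** That would remove the contradiction, but PFS would still add nothing to OS for never-responders.

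**It is only a descriptive curve.** True: non-response also shows in the response rate, and OS is reported separately. That limits the severity but does not correct a named secondary endpoint.

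**Conclusion.** The concern holds. As written, PFS omits the failure-to-respond limb of the protocol's own progression definition, and a patient who never responds has PFS equal to OS. This rests on reading relapse as following a remission, which is how the plan uses it in CRd and RFS.

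Up to 14 of 25 (45% CR/CRi) or about 16 of 25 (35%) could be affected, fewer once PR/MLFS relapses and early deaths are allowed for. Neither the number who would change treatment nor the shift in the reported curve can be derived from the documents; the 6-month gap above is an illustration on assumed survival.

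The harm is confined to the reported Kaplan-Meier PFS and its interpretation. It should be fixed before PFS is analysed, so that the event definition is not chosen with outcomes in view.

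**What to change.** In section 8.0, define PFS as time from treatment start to the first of relapse, progression as in 9.1.10 (naming failure to respond that requires a change in treatment), or death from any cause. Keep censoring at last follow-up for patients without an event.

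Add one dating rule: failure to respond is dated at the section 5.3 marrow or blood assessment that establishes the non-response or progression leading to the change in treatment. Because marrows may be repeated every 2 weeks, the rule should say which one counts if several show non-response. State whether recurrence after PR or MLFS is an event.

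Separately, sections 4.0 and 4.1.1.2 conflict on whether a patient below MLFS after cycle 2 leaves or may continue, and must be reconciled. The wording of the PFS clause does not depend on which rule is kept, although the timing of recorded treatment changes may.

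The cost is one event clause and a few sentences. Reported PFS will be no longer than before, and shorter if any non-responder fails before death. Non-response on treatment is already assessed under 5.3 item a, and the need for alternative treatment is already an off-study reason in 4.3. Treatment changes made after a patient leaves study need extra recording, because item b covers only relapse and survival. This may be common, since section 4.2 bars most other anti-leukemia therapy on study.

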5.1 During Treatment Evaluation (Cycle 1)

- a. Physical examination (including vital signs) 3 times per week.
- b. CBC with differential (differential not required if WBC $\leq 0.5 \times 10^9/L$), 3 times per week (or as clinically indicated) until remission, then every 2 to 4 weeks during active treatment, and then every 4 to 8 weeks thereafter as long as they are on study.
- c. Serum chemistry profile (including uric acid) 3 times per week for the first 4 weeks and then every 2 to 4 weeks during active treatment.
- d. Biomarker testing for correlative studies on D1, 5, 10, and 12 of cycle 1 as summarized in section 5.4.
- e. Evaluation of toxicity assessment prior to each cycle.

5.2 During Treatment Evaluation (Cycle 2 and beyond).

- a. Physical examination (including vital signs, weight, performance status) prior to each cycle.
- b. CBC with differential (differential not required if WBC $\leq 0.5 \times 10^9/L$), at least 1-2 times per week (or as clinically indicated) until remission, then every 2 to 4 weeks during active treatment, and then every 4 to 8 weeks thereafter as long as they are on study.
- c. Serum chemistry profile at least once weekly until remission and then every 2 to 4 weeks during active treatment.
- d. Evaluation of toxicity assessment prior to each cycle.

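### CRd and PFS are censored at last follow-up, which may be a phone call, so unassessed time can count as relapse-free; tie the date to the last disease assessment, in both directions

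*Combined protocol and SAP*

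**What the plan says.** The analysis plan in section 8.0 gives three time-to-event endpoints one censoring date. PFS is "the time interval between treatment start and the date of death, relapse or last follow-up, whichever occurred first". CRd, among patients with CR or CRi, is "the time interval between the date of CR/CRi and the date of disease relapse, death or last follow-up, whichever occurred first". OS also ends at death or last follow-up. The estimator is stated once for all three: "Kaplan-Meier method will be used to assess OS, CRd and PFS probabilities". Nowhere is last follow-up defined, for CRd or PFS, as a date on which the disease was assessed.

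Three other provisions decide what that date can be:

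- Section 5.3b: "Patients will be followed for relapse and survival every 6 to 12 months after completion of active treatment and while still on study", with enrolment on the department's long-term umbrella protocol as the alternative. It adds: "This may be completed by phone call if the patient is not coming for routine visits".
- Section 5.3a: marrows continue "as required by leukemia evolution until remission or non-response". None is scheduled for a patient in remission.
- Section 5.1 (Cycle 1), item b, repeated in 5.2, item b: blood counts every 2 to 4 weeks during active treatment after remission, "then every 4 to 8 weeks thereafter as long as they are on study".

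Section 9.1.8 defines a closely related endpoint, RFS, and requires objective documentation before a relapse counts as an event. It gives no censoring date.

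**The concern.** For OS the date is right: a phone call establishes that the patient is alive. For CRd and PFS the same call can carry a patient forward as relapse-free when no count or marrow supports it. If the documentation standard in 9.1.8 applies to relapse generally, the rule is lopsided, because a call cannot by itself establish a relapse but can extend relapse-free time.

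A relapse during an unassessed stretch is then either never counted or enters only as a death, at a later date. Both push the Kaplan-Meier curve upward. With few responders (section 8.0 illustrates 11 responses among 25 phase II patients), a handful of patients censored at a call could shape the later part of the CRd curve.

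**Working it through.** **No figure to reproduce.** The documents give no event count, power, target or expected median for CRd or PFS. The check is a worked patient and an illustrative simulation of CRd.

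**One patient.** CR at month 1, last clean count and marrow at month 7, phone contact at month 18 with no laboratory data.

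- CRd as written: 18 - 1 = 17 months, censored. Documented relapse-free time: 7 - 1 = 6 months.
- PFS as written: 18 months. Documented: 7 months.
- The unassessed gap is 18 - 7 = 11 months, about 48 weeks. An on-study patient should have had between 48/8 = 6 and 48/4 = 12 counts in it, so this example needs missed counts or a patient who has left the on-study schedule.

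**Simulation inputs**

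- Relapse times exponential. Median 14.7 months (section 2.3, remission duration on the backbone in older newly diagnosed AML), with 6 months as a lower assumption.
- Relapse to death exponential, median 4.2 months. This borrows the ts-AML median OS in section 2.12 as a stand-in.
- Calls every 6 or 12 months (section 5.3b).
- Assumed, because the documents are silent: 25% or 50% of responders followed by phone only with no further counts, and calls that miss none, half or all relapses. A reported relapse is dated correctly; a missed one becomes an event only at death.

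The simulated true median itself varies from 14.6 to 14.8 between runs, so differences of 0.1 month are noise.

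**Set-up A: phone-only from 5 months after CR, data cut at 12-36 months, calls every 6 months.** True median 14.7, true 12-month rate 0.568. The last column censors phone-negative patients at the last laboratory assessment while still counting phone-reported relapses and deaths.

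| Phone share | Relapses missed | As written: median, 12-month | Date moved, reports still counted: median, 12-month |
|---|---|---|---|
| 25% | none | 14.9, 0.571 | 13.6, 0.544 |
| 25% | half | 15.3, 0.583 | 13.9, 0.554 |
| 25% | all | 16.0, 0.598 | 14.4, 0.568 |
| 50% | none | 15.0, 0.574 | 12.4, 0.511 |
| 50% | half | 15.8, 0.597 | 13.1, 0.533 |
| 50% | all | 17.3, 0.630 | 14.1, 0.569 |

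With up to half of relapses missed, the written rule adds 14.9 - 14.7 = 0.2 to 15.8 - 14.7 = 1.1 months. If every relapse is missed it adds 16.0 - 14.7 = 1.3 to 17.3 - 14.7 = 2.6 months.

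**Set-up B: laboratory monitoring ends 5.5-9.7 months after CR, data cut at 12-30 months, same phone shares.**

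- As written: median 14.7-16.7 months, so a shift of 0 to 2.0. The 12-month rate is 0.571-0.608, a shift of 0.3 to 4.0 points.
- Last assessment, undocumented phone reports ignored in both directions, later deaths counted: 14.0-14.4 months and 0.564-0.568.
- Last assessment, phone-reported relapses counted while phone-negative patients are pulled back: 12.7-14.4 months.

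**Shorter remissions.** With a true median of 6.0 months, 50% by phone and 6-month calls, set-up A gives 6.3, 6.5 or 6.8 months as calls miss none, half or all relapses. The 12-month rates are 0.257, 0.287 and 0.332 against 0.251.

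**Why one-sided counting fails.** Pulling back only the patients whose calls were negative removes event-free people from the risk set and keeps the events. That is informative censoring, and it makes CRd read short.

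**Precision.** With 11 responders and a 12-month rate of 0.57, the 95% half-width before censoring is 1.96 × √(0.57 × 0.43 / 11) = 0.29, far larger than a shift of 0 to 4 points.

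**The case against.** The strongest reply is that the plan already contains most of the protection. Blood counts are required every 4 to 8 weeks while a patient is on study, so last follow-up should normally sit within about 8 weeks of a count. The 5.3b contact is made for relapse as well as survival, so a relapse known to the patient can be picked up. The phone option is confined to patients not attending visits. CRd and PFS are secondary and descriptive, with no test, target or stopping rule attached.

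All of this stands, and it limits the size. It does not close the gap. The count schedule lasts only while the patient is on study, 5.3b allows transfer to an umbrella protocol whose schedule is not shown, and patients who do not attend are the ones least likely to have counts. If the counts are done, the better censoring date costs almost nothing; if they are not, it is needed.

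A reader might go further and infer that both endpoints will read too long. The documents do not support that: neither the phone share nor the proportion of relapses missed is given. PFS was not simulated; the same mechanism applies there, diluted by events during treatment. A reader might also infer that moving the date alone restores the true curve. It does not while later phone-reported relapses or deaths still count.

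**Conclusion.** The point holds as a correctable weakness in the definitions. Section 8.0 permits unassessed time to count as relapse-free, and any bias from that route lengthens CRd and PFS. The likely size is about 0 to 2 months on a 14.7-month median and 0 to 4 points at 12 months. This assumes that 25-50% of responders are followed by phone, that laboratory monitoring ends 5.5-9.7 months after CR, and that median survival after relapse is 4.2 months. Earlier loss of monitoring with every relapse missed gives more (2.6 months in set-up A). The shift is close to zero if the 4-8 weekly counts are kept and relapse dates are retrieved. No decision rule is affected. The matter is minor, but the rule should be fixed before analysis so that the date is not chosen after the data are seen.

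**What to change.** In section 8.0:

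1. Keep last known alive as the censoring date for OS only.
2. For CRd and PFS, censor patients without an event at the last disease assessment that showed no relapse: a marrow, or a blood count without circulating blasts.
3. Apply the rule in both directions. A phone contact neither extends relapse-free time nor counts as a relapse unless a dated blood count or marrow report supports it.
4. State how deaths after a gap in assessments are counted. Counting them as events is defensible but leaves a median of 14.0-14.4 against 14.7 months in set-up B. The true median is recovered only if every event after monitoring stops is set aside, which discards observed deaths.
5. Report a sensitivity analysis using last contact.
6. State that outside counts and marrow reports may be retrieved after treatment. Section 5.5 provides for outside records only during treatment.

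The cost is a few sentences and some record retrieval, with no new visits. Some censoring times become shorter, late-curve intervals widen slightly, and a small downward bias in the median can remain if deaths after a gap count as events.
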